#### 8.6.1 IOL REPOSITIONING

If IOL repositioning is required, it should be done in the early postoperative period, preferably within the first 30 days following surgery. Repositioning should only be considered in cases when tilt or decentration is such that repositioning is necessary to improve the visual outcomes of the subject or prevent damage to the eye.

#### 8.6.2 IOL EXPLANTATION AND REPLACEMENT

If IOL explantation and replacement is required, it should be done in the early postoperative period. In the case of an incorrect IOL power or residual refractive error, if IOL replacement is expected to improve the subject's visual outcomes, the IOL should be replaced with a new lens; however, the replacement IOL cannot be the investigational IOL model.

In the case where the subject reports visual disturbances in the early postoperative period, the surgeon should remind the subject that these symptoms generally improve over time due to neural adaptation. Therefore, adequate time should be allowed for this neural adaptation to occur. The Investigator should consult with the Medical Monitor and carefully consider the potential risks and benefits of the SSI. These should be discussed with the subject; if the subject is intolerant of persistent visual disturbances and the Investigator identifies the IOL properties as being the primary cause then lens replacement should be considered.

### 8.7 ADVERSE EVENTS, SERIOUS ADVERSE EVENTS, UNANTICIPATED ADVERSE DEVICE EFFECTS AND DEVICE DEFICIENCIES

#### 8.7.1 DEFINITION OF ADVERSE EVENTS

An adverse event (AE) is any untoward medical occurrence, unintended disease or injury, or untoward clinical sign (including an abnormal laboratory finding) or symptom in subjects whether or not related to an investigational device.

## 8.7.2 DEFINITION OF SERIOUS ADVERSE EVENTS

A serious adverse event (SAE) is defined as any untoward medical occurrence that meets any of the following:

- Is associated with a loss of 2 or more lines of BCDVA [loss of 10 or more Early Treatment Diabetic Retinopathy Study (ETDRS) letters] at Visit 4 or later from any prior postoperative visit
- Requires inpatient hospitalization or prolongation of existing hospitalization;
- Requires medical or surgical intervention to preclude permanent impairment of a body function or permanent damage to a body structure;
- Is life threatening (places the subject at immediate risk of death from the event as it occurred) or sight threatening;
- Results in permanent impairment of a body function or permanent damage to a body structure;
- Results in death;
- May jeopardize the subject and require medical or surgical intervention to prevent one of the other outcomes.

### 8.7.2.1 CUMULATIVE ADVERSE EVENTS

In addition, the total number of the following adverse events that have occurred at any time will be reported as cumulative AEs, consistent with categories provided in ISO 11979-7:

- Cystoid macular edema
- Hypopyon
- Endophthalmitis - defined as intraocular inflammation leading to diagnostic vitreous tap and intraocular antibiotics
- Lens dislocation from posterior chamber
- Pupillary block - shallowing of anterior chamber due to obstruction of aqueous humor flow from the posterior to anterior chamber through the pupil by the crystalline lens, vitreous face, or implanted device
- Retinal detachment
- Secondary surgical intervention (excluding posterior capsulotomies)

### 8.7.2.2 PERSISTENT ADVERSE EVENTS

The total number of the following adverse events that are present at the conclusion of the clinical investigation will be reported as persistent AEs, consistent with categories provided in ISO 11979-7:

- Corneal stromal edema
- Cystoid macular edema
- Iritis

- Raised intraocular pressure (IOP) requiring treatment

---

### 8.7.3 DEFINITION OF ADVERSE DEVICE EFFECTS AND UNANTICIPATED ADVERSE DEVICE EFFECTS

An Adverse Device Effect (ADE) is any adverse event related to the use of a study device. This definition includes any events resulting from insufficient or inadequate instructions for use, deployment, implantation, installation or operation, or any malfunction of the device. This definition also includes any event resulting from use error or from intentional misuse of a study device.

An Unanticipated Adverse Device Effect (UADE) is any serious adverse effect on subject health or safety, or any life-threatening problem or death caused by or associated with the investigational device, if that effect, problem, or death was not previously identified in nature, severity, or degree of incidence in the study protocol.

---

### 8.7.4 CLASSIFICATION OF AN ADVERSE EVENT

#### 8.7.4.1 SEVERITY OF EVENT

The investigator must determine the intensity of the event.

Mild	Awareness of sign or symptom, but easily tolerated
Moderate	Discomfort enough to cause interference with normal daily activities
Severe	Inability to perform normal daily activities

#### 8.7.4.2 RELATIONSHIP TO STUDY INTERVENTION

All adverse events (AEs) must have their relationship to study intervention assessed by the Investigator based on temporal relationship and his/her clinical judgment. The degree of certainty about causality will be graded using the categories below.

#### Relationship of the AE to Study Device or Surgical Procedure:

Definite	A clear-cut causal relationship and no other possible cause
Probable	A causal relationship is likely although alternate etiologies are also possible
Possible	A causal relationship is not definite, alternate etiologies are also possible
Not Related	The AE has no causal relationship and/or there is evidence of alternative etiology such as concurrent medication or illness.

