#### 8.7.5 ADVERSE EVENT REPORTING

All AEs that occur during or after the Preoperative Visit through completion of study participation must be documented. Adverse events are collected from time of informed consent, and may be determined by evaluating the following in relation to the study subject:

- Observed or volunteered problems
- Complaints
- Physical signs and symptoms
- The occurrence of a medical condition during the study, which was absent at baseline
- The worsening of a baseline medical condition during the study

Each subject eye must be examined for the presence/absence of adverse events at all visits, whether scheduled or not. If an AE occurs, the first concern will be the safety and welfare of the subject; treatment should be provided as appropriate for the event.

AEs, regardless of causal relationship, must be assessed by the Investigator and recorded in the subject's CRF. AEs should be recorded in the form of a diagnosis, rather than signs and symptoms. Each AE must be described as ocular or non-ocular along with the following information: date of onset, date of resolution, severity, nature of the event (intermittent, continuous), action taken (none, medical and/or surgical), relationship to study device and surgical procedure, seriousness criteria and expectedness. Any medication or other intervention necessary for the treatment of an AE must be recorded on the appropriate eCRF. If the same type of AE occurs multiple times, each event should be recorded separately.

AEs will be documented beginning at the time of onset, and documentation must continue until recovery is noted. Events that are ongoing at the time of study exit should be followed until resolution or stabilization.

Ocular conditions or diseases noted during the Preoperative Visit that are chronic but stable and meet the inclusion/exclusions criteria should be recorded as Ocular History in the subject's case report form.

The worsening of a preoperative condition or disease will be considered an AE. As applicable, signs and symptoms indicating a common underlying pathology should be noted as one comprehensive event.

---

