### **Adverse Events**

Analyses of adverse events will be performed separately for first operative eyes, second operative eyes, and all operative eyes.

The incidence of operative eyes with at least one serious adverse event will be summarized using categorical summary statistics by treatment received.

Cumulative and persistent adverse events from ISO 11979-7 Table E.2 will be summarized using descriptive statistics by AE type and treatment and will be compared to the maximum number of cases allowed before the ISO SPE rate is exceeded. Additionally, cumulative and persistent adverse events will be summarized separately by age group (< 65 years vs.  $\geq$  65 years) and by investigator.

The incidence of adverse events based on consensus definitions as set forth by the American Academy of Ophthalmology's Task Force (Masket et al. Ophthalmology 2017) will be summarized by treatment group.

All types of adverse events will be reported and compared between arms using descriptive statistics. Separate analyses will be done for device-related events and events that are of moderate to severe severity. All adverse events reported will be summarized and listed by subject.

Adverse events will also be summarized for all ocular AEs and for all SAEs. All ocular AEs will also be summarized by maximal severity, for AEs related to the study lens, and by study day of onset.

In addition, the following summaries will be provided:

- Ocular AEs by relationship to study device/procedure as well as unrelated Ocular and Non-ocular AEs
- Ocular Serious AEs by relationship to study device/procedure as well as unrelated Ocular and Non-ocular Serious AEs
- Ocular AEs by maximal severity
- Ocular AEs by age group (< 65 years vs.  $\geq$  65 years)
- Ocular AEs by investigator

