### **15.3 Adverse Events**

[figure not shown]
Adverse events (AEs) will be coded using MedDRA Version 24.1.

Non-ocular treatment-emergent adverse events (TEAE) include all AEs occurring or worsening during or after the first eye operation. Ocular TEAEs for a respective eye will include all AEs occurring or worsening during or after the operation for the respective eye.

TEAEs based on consensus definitions as set forth by the American Academy of Ophthalmology (AAO)'s Task Force will be summarized by treatment group using discrete summary statistics. Separate summaries will be provided for first operative eyes, second operative eyes, and all operative eyes.

An overall summary will be presented that includes the number and percentage of subjects who experienced at least one event by treatment group for the following AEs:

- TEAEs
- Ocular TEAEs
- Non-ocular TEAEs
- Treatment-emergent Serious Adverse Events (TE-SAEs)
- Ocular TE-SAEs
- Non-ocular TE-SAEs
- Ocular device-related TEAEs
- Ocular TEAEs by strongest relationship to study device
- Ocular TEAEs by strongest relationship to surgical procedure
- Ocular TE-SAEs by strongest relationship to study device
- Ocular TE-SAEs by strongest relationship to surgical procedure

- Ocular TEAEs of moderate to severe severity
- Ocular TEAEs by maximum severity
- Ocular TEAEs by study day of onset
- Ocular TEAEs by age group (< 65 years vs  $\geq$  65 years)
- Ocular TEAEs by pre-operative photopic pupil size (Small [ $<$  2.5 mm], Medium [2.5 to  $\leq$  4 mm], Large [ $>$  4 mm])
- Ocular TEAEs by site
- TEAEs leading to discontinuation from study
- TEAEs leading to death

For the summary of ocular TEAEs by pupil size, the average pupil size computed over both eyes will be used to determine the pupil size subgroup.

In addition, the following summaries by SOC, PT, and treatment group will be provided at eye level (first operative eyes, second operative eyes, and all operative eyes separately) or subject level as appropriate:

- Ocular TEAEs
- Non-ocular TEAEs
- Ocular TE-SAEs
- Non-ocular TE-SAEs
- Ocular TEAEs related to study device
- Ocular TEAEs related to surgical procedure
- Ocular TEAEs by maximal severity

In the summaries, SOCs are listed in alphabetical order, and PTs within an SOC are listed in order of descending frequency for FINEVISION HP treatment.

[figure not shown]
All AEs and all TE-SAEs will be presented in separate listings.

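### The Not Related grade can be met by evidence of another cause alone, so it overlaps Probable and Possible and adverse device effects can be understated; the visible SAP relatedness summaries also cover ocular events only

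*Protocol*

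**What the plan says.** Protocol 8.7.4.2 requires the relationship of every AE to be "assessed by the Investigator based on temporal relationship and his/her clinical judgment". Three of the four grades matter here:

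- *Not Related*: "The AE has no causal relationship and/or there is evidence of alternative etiology such as concurrent medication or illness".
- *Probable*: "A causal relationship is likely although alternate etiologies are also possible".
- *Possible*: the link is uncertain, and here too another cause may be at work.

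No rule says which grade applies when an event meets more than one definition.

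The grade feeds the definition in Protocol 8.7.3: "An Adverse Device Effect (ADE) is any adverse event related to the use of a study device". That definition is not limited to the eye. Protocol 8.7.5 has each AE described as ocular or non-ocular and, among other items, its "relationship to study device and surgical procedure, seriousness criteria and expectedness" recorded.

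On analysis, the adverse-event part of Protocol 9.4.6 states: "Separate analyses will be done for device-related events and events that are of moderate to severe severity". The itemised list that follows asks for ocular AEs (and ocular serious AEs) by relationship, and mentions non-ocular events only together with the word unrelated. In SAP 15.3 every visible relatedness item is ocular: the row "Ocular device-related TEAEs", the rows by strongest relationship to device and to procedure, and the tables by system organ class and preferred term for events related to device or procedure. Non-ocular TEAEs and serious TEAEs are tabulated without relationship, and all AEs are listed. The visible text of SAP 15.3 does not say which of the four grades count as device-related.

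**The concern.** A causality scale should put each event in one grade. Here an event can have evidence of another cause and still be a likely effect of the lens. Two investigators could then grade it Probable and Not Related, both following the text.

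The situation is realistic in this trial. Protocol 2.3.1 associates multifocal lenses with glare, halos and reduced contrast sensitivity, and 8.7.7 lists these as anticipated events. Exclusion criterion 9 names severe dry eye as an example, so eyes with milder dry eye may be enrolled, and Protocol 8.6 treats dry eye as a non-optical explanation when judging surgical re-intervention. Glare in such an eye could meet both grades. The person grading is the investigator, and Protocol 6.3 reserves masking of site staff for those who assess visual performance, so the choice between two permitted grades is not protected by masking.

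At stake are the count of adverse device effects, the device-related rates in the SAP tables and, less directly, the recognition of an unanticipated adverse device effect. For a non-ocular serious event that recognition affects timing: Protocol 8.7.6 gives 24 hours for an unanticipated device effect and 7 days for other non-ocular serious events.

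**Working it through.** The documents give no figure to reproduce, so the first checks are logical.

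**1. Overlap of the grades.** Take an event for which the device is a likely cause and there is also evidence of another cause.

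- *Probable*: the link is likely, and other causes are allowed. Met.
- *Not Related*, first limb (no causal relationship): not met.
- *Not Related*, second limb (evidence of another cause): met. With and/or, one limb is enough. Met.

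Both grades apply. If the link is merely not definite, the same reasoning gives Possible and Not Related together.

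**2. Would a plain *and* repair it?** Take an event with no causal link and no identified other cause. With *and*, the second limb fails, so Not Related is not met. Definite and Probable do not fit either, and the event drifts into Possible. The plain swap removes one fault and creates another.

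**3. Coverage of relatedness across the documents.**

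- Definition (Protocol 8.7.3): any related AE, ocular or not.
- Collection (Protocol 8.7.5): relationship recorded for every AE.
- Protocol 9.4.6, general sentence: device-related events, no ocular limit.
- Protocol 9.4.6, itemised list: ocular events by relationship; unclear for non-ocular events.
- SAP 15.3, visible text: ocular events only. SAP section 1 says the SAP methods supersede those in the protocol.

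**4. Size, as an illustration only.** Let r be the true proportion of eyes with a device-related event, and f the share of those graded Not Related because of another cause. The reported rate is (1 − f) × r. The relative loss is f: none at f = 0, 10% at f = 0.1, 30% at f = 0.3.

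Assume r = 10% in the 334 planned test-arm first eyes, that is 33.4 eyes:

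- f = 0.25: 33.4 × 0.75 = 25.05 eyes; 25.05 / 334 = 7.5%.
- f = 0.50: 33.4 × 0.50 = 16.7 eyes; 16.7 / 334 = 5.0%.

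Both r and f are assumptions; neither is in the documents. If f is the same in both arms, the ratio of the rates is unchanged and their difference shrinks by the factor (1 − f). If f differs between arms, the comparison can move either way.

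**5. What does not depend on the scale.** The surgical-intervention endpoint has its own attribution rule, with the Medical Monitor consulted when attribution is uncertain (Protocol 8.6). The ISO cumulative and persistent counts state no relatedness condition (SAP 15.2), nor do the summaries by consensus definitions (SAP 15.3). QoV and contrast sensitivity are measured in both arms without causality grading (SAP 15.1 and 15.2). Ocular serious AEs are reported within 24 hours whatever their grade (Protocol 8.7.6).

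**The case against.** The best defence of the scale is that Probable and Possible speak of other causes being possible, whereas Not Related asks for evidence of one. That can be read as a higher bar, and a careful investigator could grade consistently with it. The scale is also the same in both arms. This stands as a reason not to assume that misgrading will happen. It does not remove the overlap, because evidence of another cause can coexist with a likely device effect.

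Two stronger readings are tempting, and the documents do not support them.

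- *Non-ocular device effects vanish from the report.* They do not. SAP 15.3 tabulates non-ocular TEAEs and serious TEAEs by treatment group and lists all AEs, so an excess in the test arm would still be visible. Only the breakdown by relationship is absent.
- *The SAP silently narrowed the protocol's plan.* This is not established. The itemised list in Protocol 9.4.6 is itself ambiguous on non-ocular events, and the SAP's ocular rows are compatible with it. Part of SAP section 19 is redacted and the table list in section 22 is not shown, so neither a declared change nor a further table can be ruled out.

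It is also fair to say that no hypothesis test depends on either matter.

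**Conclusion.** The point holds in a limited form. The wording of Not Related permits an event that meets Probable or Possible to be graded Not Related, with no rule to decide between them, so adverse device effects can be understated. A reader might go further and infer that they are undercounted. The documents show no such result: they contain no misgrading rate, and the fall from 10% to between 7.5% and 5.0% rests wholly on assumed values.

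The second part is a gap in presentation. The definition and the data collection cover all events, but the visible relatedness summaries cover ocular events only, and the grades that count as related are not stated. This conclusion is limited to the visible text of SAP 15.3.

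The reach of both parts is the relatedness summaries and the classification of adverse device effects and unanticipated adverse device effects. The latter has its own definition in Protocol 8.7.3, based on being caused by or associated with the device, so the four-grade scale bears on it only indirectly. The effectiveness endpoints and the primary and secondary safety endpoints are unaffected.

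**What to change.** In Protocol 8.7.4.2, make the grades mutually exclusive. Define Not Related as no reasonable possibility of a causal relationship to the device or procedure, for example because another cause fully explains the event. State that evidence of another cause does not by itself give this grade. Unlike a plain change to *and*, this leaves a home for an event that is clearly unrelated but has no identified cause.

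In SAP 15.3, state that Definite, Probable and Possible count as related. Beside the ocular rows, add all and non-ocular TEAEs and serious TEAEs by relationship to device and to procedure. If the sponsor prefers ocular-only summaries, record that choice with its reason in SAP section 19.

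The cost is a wording change in the protocol or the CRF guidance and a few table rows from data already collected. The downside is that device-related rates may look slightly less favourable.

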#### 8.7.5 ADVERSE EVENT REPORTING

All AEs that occur during or after the Preoperative Visit through completion of study participation must be documented. Adverse events are collected from time of informed consent, and may be determined by evaluating the following in relation to the study subject:

- Observed or volunteered problems
- Complaints
- Physical signs and symptoms
- The occurrence of a medical condition during the study, which was absent at baseline
- The worsening of a baseline medical condition during the study

Each subject eye must be examined for the presence/absence of adverse events at all visits, whether scheduled or not. If an AE occurs, the first concern will be the safety and welfare of the subject; treatment should be provided as appropriate for the event.

AEs, regardless of causal relationship, must be assessed by the Investigator and recorded in the subject's CRF. AEs should be recorded in the form of a diagnosis, rather than signs and symptoms. Each AE must be described as ocular or non-ocular along with the following information: date of onset, date of resolution, severity, nature of the event (intermittent, continuous), action taken (none, medical and/or surgical), relationship to study device and surgical procedure, seriousness criteria and expectedness. Any medication or other intervention necessary for the treatment of an AE must be recorded on the appropriate eCRF. If the same type of AE occurs multiple times, each event should be recorded separately.

AEs will be documented beginning at the time of onset, and documentation must continue until recovery is noted. Events that are ongoing at the time of study exit should be followed until resolution or stabilization.

Ocular conditions or diseases noted during the Preoperative Visit that are chronic but stable and meet the inclusion/exclusions criteria should be recorded as Ocular History in the subject's case report form.

The worsening of a preoperative condition or disease will be considered an AE. As applicable, signs and symptoms indicating a common underlying pathology should be noted as one comprehensive event.

---

#### 8.7.6 EXPEDITED ADVERSE EVENT REPORTING

Any ocular SAE or UADE, whether the event is expected or unexpected, ***must be reported to the Sponsor, or the Sponsor's designee, within 24 hours*** of the Investigator becoming aware of the event. Non-ocular SAEs must be reported within 7 days.

SAEs and UADEs must be recorded in the subject's eCRF. Information provided on the eCRF should be supplemented with hospitalization records, death certificate, clinic notes from specialists evaluating the subject's condition, etc. as applicable for the event. The urgency for reporting SAEs/UADEs is 3-fold:

- To facilitate discussion [and implementation, if necessary] by the Sponsor and the Investigator of appropriate follow-up measures;
- To facilitate Investigator reporting of unanticipated problems involving risk to human subjects to the IRB; and
- To enable the Sponsor to fulfill the reporting requirements to the appropriate regulatory authority.

It is the responsibility of the Investigator to promptly notify the IRB of SAEs per the IRBs reporting requirements. Investigators must report the occurrence of a UADE to their reviewing IRB as soon as possible, but no later than 10 working days after first learning of the event. The Sponsor must report the results of an evaluation of an UADE to FDA and all reviewing IRBs and participating investigators within 10 working days after the Sponsor first receives notice of the effect.

---

